## 8. SELECTION AND WITHDRAWAL OF PATIENTS

Patients eligible for enrollment in the study must meet all of the following inclusion criteria and none of the exclusion criteria.

## 8.1. Patient Inclusion Criteria

- 1. Written informed consent, and authorization for release and use of protected health information.
- 2. Between 18 and 65 years of age, inclusive, at the time of informed consent.
- 3. Definitive diagnosis of alopecia areata with a current episode of scalp hair loss lasting at least 6 months and not exceeding 10 years at the time of Screening. Total disease duration greater than 10 years is permitted.
- 4. At least 50% scalp hair loss, as defined by a SALT score ≥50, at Screening and Baseline.
- 5. If of reproductive age, female participants and female partners of male participants, willing and able to use a medically highly effective form of birth control from at least 4 weeks prior to Baseline until at least 30 days following last dose of study drug. Examples of medically highly effective forms of birth control are:
  - a. Confirmed infertility due to surgical procedure
  - b. Post-menopausal (cessation of menses for at least 12 months prior to screening)
  - c. Infertility of sexual partner or partner of the same sex
  - d. Implants of levonorgestrel in females
  - e. Contraceptive (combined oral, patch, vaginal ring, injectable, implant) in females
  - f. Double-barrier method (any combination of physical and chemical methods)
  - g. Intrauterine device with a failure rate less than 1% per year
- 6. Male participants must:
  - a. Agree to use, with their partners, one of the highly effective contraceptive methods listed in Inclusion Criterion 5, from Baseline until at least 30 days following last dose of study drug.
  - b. Refrain from donating sperm during the study and for at least 30 days after the end of the study.
- 7. Willing to comply with the study visits and requirements of the study protocol.

## 8.2. Patient Exclusion Criteria

- 1. History or presence of hair transplants.
- 2. Treatment with other medications or agents within 1 month of Baseline or during the study that may affect hair regrowth or immune response, including but not limited to: corticosteroids administered orally, intravenously or intramuscularly, or applied to areas of skin affected by alopecia (intranasal and inhaled corticosteroids are allowed, eye and ear drops containing corticosteroids are also allowed); oral retinoids, oral cyclines

- (minocin, tetracycline); platelet-rich plasma injections; topical application to affected areas of retinoids, anthralin, squaric acid, diphenylcyclopropenone, or minoxidil.
- 3. Treatment with systemic immunosuppressive medications including but not limited to methotrexate, cyclosporine, azathioprine, chloroquine derivatives, etanercept, JAK inhibitors within 3 months of Screening or during the study.
  - NOTE: Patients previously treated with a Janus Kinase inhibitor more than 3 months prior to Screening may be allowed to enter the study at the discretion of the PI, if their previous treatment with a JAK inhibitor was well tolerated, and subsequent JAK treatment would not be thought to put the subject at risk. Consultation with the Medical Monitor may be warranted should questions arise with regard to prior tolerability.
- 4. Treatment with biologics (e.g., adalimumab, atlizumab, canakinumab, certolizumab, fontolizumab, golimumab, infliximab, mepolizumab, rituximab, secukinumab, tocilizumab, ustekinumab) within 6 months of Screening or during the study.
- 5. Active scalp inflammation, psoriasis, or seborrheic dermatitis requiring topical treatment to the scalp, significant trauma to the scalp, or other scalp condition that may interfere with the SALT assessment, or untreated actinic keratosis anywhere on the body at Screening and/or Baseline.
- 6. Known history of moderate to severe androgenic alopecia or female pattern hair loss prior to alopecia areata.
- 7. Unwilling to maintain a consistent hair style, including shampoo and hair products (including hair dye, process, and timing to hair appointments), and to refrain from weaves or extensions throughout the course of the study, or shaving of scalp hair for 2 weeks preceding a SALT assessment.
- 8. Use of adhesive wigs, other than banded perimeter wigs, during the study.
- 9. History of a lymphoproliferative disease or malignancy, other than non-melanoma skin cancer or cervical carcinoma. Patients with 3 or more basal or squamous cell carcinomas diagnosed in the past 2 years are excluded.
- 10. History of solid organ or hematological transplantation.
- 11. Fever, inflammation, or systemic signs of illness suggestive of systemic or invasive infection or a positive SARS-CoV-2 test result within 2 weeks prior to Baseline.
- 12. Abnormal levels of thyroid stimulating hormone at Screening, defined as <0.9 x the lower limit of normal (LLN) and >1.5 x the upper limit of normal (ULN).
- 13. Screening labs outside the normal range for parameters associated with potential risk for treatment under investigation. This will include but is not limited to:
  - a) Platelets  $<100 \times 10^9/L \text{ or } > 600 \times 10^9/L$
  - b) Absolute neutrophil count  $\leq 1.5 \times 10^9/L$
  - c) Hemoglobin levels ≤10.5 g/dL for females, or hemoglobin levels ≤12.0 g/dL for males
- 14. Screening blood level of hemoglobin A1c ≥7.5% (58 mmol/mol, 9.3 mmol/L).

- 15. Abnormal liver function at Screening, defined as  $\ge 2 \times ULN$  of serum alanine transaminase, serum aspartate transaminase, and serum alkaline phosphatase, or  $\ge 1.5 \times ULN$  total bilirubin (unless isolated Gilbert's syndrome).
- 16. Abnormal renal function (estimated glomerular filtration rate <60 mL/min/1.73 m2 using the CKD-EPI 2009 equation) at Screening.
- 17. Patient has positive results for hepatitis B surface antigens (HBsAg), antibodies to hepatitis B core antigens (anti-HBc), or hepatitis C virus (HCV) at Screening, or known history of human immunodeficiency virus infection. Subjects who test positive for HCV but who are in remission (sustained virologic response as evidenced by undetectable HCV RNA level using a sensitive assay≥ 12 weeks after completion of HCV therapy) are allowed inclusion in the study.
- 18. Vaccination with a live attenuated vaccine during the study or up to 6 weeks prior to randomization.
- 19. History of previous active disease due to *M. tuberculosis* (TB) without documentation of successful treatment; OR, patient has a positive result from a Tuberculin Skin Test (TST) or a QuantiFERON-TB Gold (QFT) test performed at Screening.
  - NOTE: If the patient has a positive QFT result at Screening and: (1) has no history of successful treatment for either active disease or latent infection due to M. tuberculosis, or (2) currently resides in an area with low prevalence of tuberculosis, or (3) has no lifetime history of occupational or household exposure to person(s) with tuberculosis, then the initial Screening QFT result may be a false-positive. In this instance, a second Screening test for latent TB infection should be obtained either: (1) a repeat QFT test or (2) a Tuberculin Skin Test (TST). The repeat QFT test must be negative or the TST should show <15mm induration (considered negative TST) before being considered eligible for the study.
- 20. History of prolonged QT syndrome or a Screening QTc interval with Fridericia's correction (QTcF) > 450 msec for males or QTcF > 470 msec for females.
- 21. History of alcohol, medication, or illicit drug abuse within 1 year before the first dose of study drug.
- 22. Females who are nursing, pregnant, or planning to become pregnant while in the study, and for 30 days after last dose of study drug.
- 23. Participation in another investigational study within the greater of 4 weeks or 5 half-lives of an investigational medication prior to screening or during the study.
- 24. Use of strong cytochrome P450 3A4 (CYP3A4) inhibitors (such as, but not limited to clarithromycin, conivaptan, grapefruit juice, indinavir, itraconazole, ketoconazole, lopinavir/ritonavir, mibefradil, nefazodone, nelfinavir, posaconazole, saquinavir, telaprevir, telithromycin, voriconazole, or fluconazole) dosed for systemic exposure.
- 25. Use of strong CYP3A4 inducers (such as, but not limited to barbiturates, carbamazepine, efavirenz, glucocorticoids, modafinil, nevirapine, oxcarbazepine, phenobarbital, phenytoin, pioglitazone, rifabutin, rifampin, St. John's Wort, or troglitazone) dosed for systemic exposure.

- 26. Donation of blood > 499 mL of blood or plasma within 56 days of Screening (during a clinical trial or at a blood bank donation) and for 30 days after last dose of study drug.
- 27. Clinically significant medical condition, psychiatric disease, or social condition, as determined by the Investigator, that may unfavorably alter the risk-benefit of study participation, adversely affect study compliance, or confound interpretation of study results.

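### The TSH exclusion joins a low limit and a high limit with 'and', so as written it excludes nobody; the liver exclusion leaves open whether one raised enzyme or all three are required

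*Protocol*

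**What the plan says.** Protocol 8 requires every enrolled patient to meet none of the exclusion criteria.

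- **Exclusion 12 (Protocol 8.2)** excludes abnormal TSH at Screening, "defined as <0.9 x the lower limit of normal (LLN) and >1.5 x the upper limit of normal (ULN". The Synopsis repeats this with the same connective.
- **Exclusion 15 (Protocol 8.2)** excludes abnormal liver function at Screening. One threshold, 2 x ULN or more, is applied to "serum alanine transaminase, serum aspartate transaminase, and serum alkaline phosphatase, or" 1.5 x ULN or more of "total bilirubin (unless isolated Gilbert's syndrome". The Synopsis reads the same.
- **Exclusion 13 (Protocol 8.2)** is a general laboratory exclusion: "Screening labs outside the normal range for parameters associated with potential risk for treatment under investigation. This will include but is not limited to" platelets, neutrophils and haemoglobin. Item 13a gives a low and a high platelet limit joined by 'or'.
- **Exclusion 27 (Protocol 8.2)** is discretionary: "Clinically significant medical condition, psychiatric disease, or social condition, as determined by the Investigator".

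Table 2, footnote 9, schedules TSH at Screening only. Protocol 10.13 makes the Investigator judge eligibility from the Screening laboratory results. No other section of the protocol, and nothing in the SAP, restates Exclusion 12 or 15 in different words.

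**The concern.** Exclusion 12 sets out to define abnormal TSH, but the set it defines is empty: a value cannot lie below a low limit and above a high limit at once. The rule works only if the reader departs from its wording.

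In Exclusion 15, 'and' joins the three enzymes and 'or' precedes bilirubin. A reader who takes the connectives at face value will think that raised enzymes alone exclude a patient only when all three are raised. Another will take the enzymes as a list of tests sharing one threshold, any of which excludes.

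What is at stake is uniform application of two safety eligibility rules at about 50 planned sites (Protocol 7.2; SAP 8.1.1 allows up to 60). Protocol 13.4 does not let investigators change the text themselves. The same patient could therefore be eligible at one site and ineligible at another, and the sponsor would have no fixed standard for deciding whether an enrolment was a deviation.

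**Working it through.** The plan attaches no figure to either criterion, so there is none to reproduce. The check is one of logic.

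**Exclusion 12**

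Inputs: the multipliers 0.9 and 1.5 and the connective, from Protocol 8.2 and the Synopsis. The only assumption is that any reference range has 0 < LLN ≤ ULN.

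1. Literal rule: exclude if TSH < 0.9 x LLN *and* TSH > 1.5 x ULN.
2. Because 0 < LLN ≤ ULN, 0.9 x LLN < LLN ≤ ULN < 1.5 x ULN.
3. A value below 0.9 x LLN is therefore always below 1.5 x ULN, and the two conditions cannot both hold.
4. Numerical confirmation: TSH from 0 to 20 in steps of 0.001 (20,001 values) was tested against five assumed LLN/ULN pairs: 0.1/1, 0.3/4, 0.4/4.5, 0.5/5 and 1/1. The documents give no reference range, so these pairs are illustrative. Of 5 x 20,001 = 100,005 combinations, 0 met the literal rule.

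**Exclusion 15**

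Inputs: the connectives in Protocol 8.2. Let A, B and C mean ALT, AST and ALP at or above 2 x ULN. Let D mean that the bilirubin part is met, that is, total bilirubin at or above 1.5 x ULN and not explained by isolated Gilbert's syndrome. Four yes/no results give 2^4 = 16 patterns.

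| Reading | Rule | Patterns excluded |
|---|---|---|
| All three enzymes | (A and B and C) or D | 8 with D, plus 1 with A, B and C but not D = 9 |
| Any one enzyme | (A or B or C) or D | 8 with D, plus 7 with at least one enzyme but not D = 15 |

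The readings differ in 15 − 9 = 6 patterns: three with exactly one enzyme raised and three with exactly two, all without D. Twelve patterns have one or two enzymes raised (6 enzyme combinations x 2 states of D). In the other 6 the patient is excluded through bilirubin whichever reading is used. These are counts of logical patterns, not of patients.

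**Other criteria in the same list**

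- 13a joins low and high platelet limits with 'or', the same two-sided structure as Exclusion 12 with a different connective.
- 17 lists its hepatitis markers with 'or'.
- 13 is open-ended but names neither TSH nor a liver enzyme.
- 27 rests on the Investigator's judgement and sets no laboratory limit.

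**Effect on the statistics**

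The sample size in Protocol 12.1 rests on response rates of 40%, 26% and 9%, groups of 110, 220 and 110, and a two-sided level of 0.025. None of these depends on how Exclusion 12 or 15 is read.

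**The case against.** The strongest reply is that nobody would apply Exclusion 12 as strict Boolean logic. It names abnormal levels in the plural and gives a low and a high limit. Since the literal reading is impossible, an investigator would take the two limits as separate abnormalities, and 13a shows the form to expect. That is a fair account of likely practice, and it limits the probable harm. It does not repair the text, because the criterion still works only for readers who set its wording aside.

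For Exclusion 15 the reply is stronger. A single threshold followed by "serum alanine transaminase, serum aspartate transaminase, and serum alkaline phosphatase" can naturally be a list of tests to which that threshold applies. This stands: the wording is ambiguous, not demonstrably wrong.

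Exclusions 13 and 27, together with the Investigator's review of Screening results, would let a careful site keep out a patient with a worrying result. They mitigate, but they supply no TSH or enzyme limit.

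A reader might infer four stronger things that the documents do not support:

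- **That the liver exclusion as a whole needs all three enzymes raised, or misses everyone with one or two raised.** It does not: bilirubin at its limit excludes by itself unless it is isolated Gilbert's syndrome.
- **That patients with abnormal TSH were in fact enrolled.** An empty literal definition is not evidence of how sites applied it, and no automated eligibility check on these criteria is described.
- **That the Per Protocol analysis is compromised.** Under SAP 7.1 the sponsor classifies deviations as major or minor before database lock. No text makes a TSH or enzyme breach automatically major, and SAP 8.2.2 calls that analysis supportive.
- **That the Synopsis and Protocol 8.2 disagree on these two criteria.** Their wording matches; both carry the same defect.

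**Conclusion.** The point holds for Exclusion 12. Taken literally it excludes 0% of patients, whatever the laboratory's range, provided only that LLN does not exceed ULN. The same text in two places makes this part of the operative rule, and with TSH scheduled only at Screening, no later scheduled test would pick up what the rule lets through.

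For Exclusion 15 the finding is narrower: an ambiguity that matters only for patients with one or two enzymes at or above 2 x ULN whose total bilirubin is below its limit, or whose raised bilirubin is isolated Gilbert's syndrome. That is 6 of 16 patterns.

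How many patients fall into either group cannot be worked out from the documents. This is a drafting defect in safety eligibility rules, worth correcting because it is cheap to correct. It does not touch alpha, power, sample size or the primary analysis. Which limits are clinically right is not judged here.

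**What to change.** 1. **Exclusion 12, Protocol 8.2 and Synopsis:** the sponsor should reconcile the wording with the criterion's stated purpose of excluding abnormal TSH, so that a single result can meet it. The two thresholds stay as they are.
2. **Exclusion 15, Protocol 8.2 and Synopsis:** state whether one raised enzyme is enough or all three are required. The thresholds and the Gilbert's exception stay as they are, and the two places should remain identical.
3. **If enrolment is complete**, which is likely given the June 2022 estimate for the last visit and the SAP date of 2022-06-29: document which reading of each criterion the sites applied. Use one stated reading when eligibility deviations are classified in the pre-lock review under SAP 7.1.

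The cost is a few words in an amendment or clarification letter or, after enrolment, a short written record and a consistent pass through the Screening TSH and liver results. No analysis has to be redesigned.

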  - NOTE: If the patient has a positive QFT result at Screening and: (1) has no history of successful treatment for either active disease or latent infection due to M. tuberculosis, or (2) currently resides in an area with low prevalence of tuberculosis, or (3) has no lifetime history of occupational or household exposure to person(s) with tuberculosis, then the initial Screening QFT result may be a false-positive. In this instance, a second Screening test for latent TB infection should be obtained either: (1) a repeat QFT test or (2) a Tuberculin Skin Test (TST). The repeat QFT test must be negative or the TST should show <15mm induration (considered negative TST) before being considered eligible for the study.
- 20. History of prolonged QT syndrome or a Screening QTc interval with Fridericia's correction (QTcF) > 450 msec for males or QTcF > 470 msec for females.
- 21. History of alcohol, medication, or illicit drug abuse within 1 year before the first dose of study drug.
- 22. Females who are nursing, pregnant, or planning to become pregnant while in the study, and for 30 days after last dose of study drug.
- 23. Participation in another investigational study within the greater of 4 weeks or 5 half-lives of an investigational medication prior to screening or during the study.
- 24. Use of strong cytochrome P450 3A4 (CYP3A4) inhibitors (such as, but not limited to clarithromycin, conivaptan, grapefruit juice, indinavir, itraconazole, ketoconazole, lopinavir/ritonavir, mibefradil, nefazodone, nelfinavir, posaconazole, saquinavir, telaprevir, telithromycin, voriconazole, or fluconazole) dosed for systemic exposure.
- 25. Use of strong CYP3A4 inducers (such as, but not limited to barbiturates, carbamazepine, efavirenz, glucocorticoids, modafinil, nevirapine, oxcarbazepine, phenobarbital, phenytoin, pioglitazone, rifabutin, rifampin, St. John's Wort, or troglitazone) dosed for systemic exposure.
- 26. Donation of blood > 499 mL of blood or plasma within 56 days of Screening (during a clinical trial or at a blood bank donation) and for 30 days after last dose of study drug.
- 27. Clinically significant medical condition, psychiatric disease, or social condition, as determined by the Investigator, that may unfavorably alter the risk-benefit of study participation, adversely affect study compliance, or confound interpretation of study results.

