| Eligibility assessment  | X   | X                            |                               |                                  |    |                          |                                    |
| Demographics  | X   | Λ                            |                               |                                  |    |                          |                                    |
| Medical history   | X   | X                            |                               |                                  |    |                          |                                    |
| Randomization   | A   | X                            |                               |                                  |    |                          |                                    |
| Complete physical examination   | X   | X                            |                               |                                  |    | X                        | Х                                  |
| Brief physical examination  | A   | A                            |                               | X                                | X  | Α                        | 74                                 |
| Height  | X   |                              |                               | 71                               | 71 |                          |                                    |
| Weight  | X   | X                            |                               | X                                | X  | X                        | X                                  |
| Pregnancy test    | X   | X                            |                               | X                                | X  | X                        | X                                  |
| Tuberculosis test   | X   |                              |                               |                                  |    |                          |                                    |
| Clinical laboratory testing   | X                               | X                            | $X^{10}$                      | X                                | X  | X                        | X                                  |
| Pharmacokinetic Sampling for Population Pharmacokinetics                            |   | X                            |                               | X                   |    | X                        |                                    |

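### In the Exclusion 19 NOTE, the connector *or* lets the absence of past TB treatment alone open a retest after a positive QFT, so residence and exposure screen out no never-treated patient

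*Protocol*

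**What the plan says.** Exclusion 19 has two limbs (Protocol, Section 8.2). The first is "History of previous active disease due to" M. tuberculosis, "without documentation of successful treatment; OR, patient has a positive result from a Tuberculin Skin Test (TST) or a QuantiFERON-TB Gold (QFT) test" at Screening being the rest of the criterion. The first limb therefore concerns past active disease only. A positive test falls under the second limb.

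The NOTE then softens the second limb for a positive QFT. It lists three circumstances:

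- Condition (1), with its link to (2): "1) has no history of successful treatment for either active disease or latent infection due to M. tuberculosis, or (2) currently resides" in a low-prevalence area.
- Condition (3), with its link to (2): "or (3) has no lifetime history of occupational or household exposure to person(s) with tuberculosis".

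If the NOTE applies, "then the initial Screening QFT result may be a false-positive", and a second test is to be obtained, either a repeat QFT or a tuberculin skin test (TST). The pass rule is: "The repeat QFT test must be negative or the TST should show <15mm induration (considered negative TST) before being considered eligible for the study".

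The NOTE in the Synopsis uses the same connectors: "or (2) currently resides in an area with low prevalence of tuberculosis, or (3) has no lifetime history". In Table 2 the row "Tuberculosis test" is marked at Screening only. The SAP does not touch on this criterion.

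**The concern.** The three conditions are there to say when a positive QFT is plausibly false. Joined by *or*, any one of them is enough. Condition (1) is relevant, because a patient treated for TB has a known past infection and the positive result is then less likely to be false. It is not sufficient, because a patient with untreated latent infection meets it just as well as a patient with a false-positive result. Residence and exposure are the items that could help to tell these two apart, and for never-treated patients the *or* switches both off.

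The outcome is also the wrong way round at one point. A never-treated patient with household or occupational exposure who lives outside a low-prevalence area is labelled a possible false positive and retested. A successfully treated patient with the same residence and exposure is the only one refused.

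What is at stake is eligibility before dosing with a JAK inhibitor, a class for which Section 10.1 mentions potential immunosuppressive properties. Untreated latent infection is not caught by the first limb of Exclusion 19, so for such a patient the criterion rests on one second test.

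**Working it through.** The plan gives no figure on this point, so there is none to reproduce. The check is a truth table.

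**Inputs** (Exclusion 19 NOTE, Section 8.2 and Synopsis), for a patient with a positive Screening QFT:

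- (1) = no history of successful TB treatment. This is true for every never-treated patient.
- (2) = lives in a low-prevalence area.
- (3) = no lifetime household or occupational exposure.

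Each is yes or no, which gives 2 × 2 × 2 = 8 profiles. Three rules are compared.

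| Profile | (1) | (2) | (3) | As written: (1) or (2) or (3) | (1) and [(2) or (3)] | All three |
|---|---|---|---|---|---|---|
| 1 | yes | no | no | opens | closed | closed |
| 2 | yes | no | yes | opens | opens | closed |
| 3 | yes | yes | no | opens | opens | closed |
| 4 | yes | yes | yes | opens | opens | opens |
| 5 | no | no | no | closed | closed | closed |
| 6 | no | no | yes | opens | closed | closed |
| 7 | no | yes | no | opens | closed | closed |
| 8 | no | yes | yes | opens | closed | closed |
| **Opens** | | | | **7 of 8** | **3 of 8** | **1 of 8** |

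**Results**

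- As written, the retest opens in 4 of 4 profiles with (1) true. Neither residence nor exposure changes the outcome for any of them.
- Condition (1) opens the retest by itself only where (2) and (3) both fail. That is profile 1, so 1 of 8. Profiles 2 to 4 would be opened by (2) or (3) anyway.
- Profiles 1 and 5 have the same residence and exposure and differ only in treatment history. The untreated patient is retested and the successfully treated one is not.
- Requiring (1) and at least one of (2) or (3) closes 7 − 3 = 4 profiles: profile 1, and the three successfully treated profiles 6 to 8.
- Requiring all three closes 7 − 1 = 6 profiles. Five of these (2, 3, 6, 7 and 8) meet (2) or (3) in their own right.

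The profiles are logical combinations and carry no weights. The documents give no TB prevalence, exposure frequency or false-negative rate for the second test, so the number of patients affected cannot be derived.

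**The case against.** The best defence is that the NOTE is a deliberately broad trigger for confirmatory testing: any circumstance that casts doubt on one positive result prompts a second test, and that test decides. Nothing in the protocol says that the conditions were meant to hold together. On this view the width of the trigger is a clinical preference.

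Much of this stands. The conditions open a retest and do not waive it. A patient whose second test is positive stays out, and so does a patient with past active TB without documented successful treatment. Exposure is not ignored elsewhere either:

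- Serious infection history and exposure risk are taken at Screening and on Day 1 (Section 10.1).
- The investigator can exclude on clinical grounds (Exclusion 27).
- Examinations look for signs of TB, and remote visits also ask about exposure (Section 10.11).
- Unscheduled visits are available for suspected TB (Section 10.14).
- Treatment can be stopped at any time (Section 8.3).

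Two things do not stand. If almost every positive QFT was meant to be retested, three conditions that refuse one profile in 8, and that one a treated patient, are a poor way to say so. And the safeguards are either a matter of judgement or act after dosing has begun. None of them puts a residence or exposure condition back into the NOTE.

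Three stronger readings are tempting, and the documents do not support them.

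- A reader might infer that exposed patients enter on a positive test alone. They do not, because the second test must be negative.
- A reader might infer that the sponsor meant *and* throughout. No section shows this. That rule would also refuse a retest to a never-treated, never-exposed patient (profile 2) only because of where the patient lives.
- A reader might blame the *or* for the absence of later scheduled TB tests. Table 2 applies to every patient and is a separate matter.

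**Conclusion.** The point holds as a defect of wording in an eligibility criterion. Condition (1) alone can open the retest, and because it is true of every never-treated patient, residence and exposure filter none of them. The profile that depends on condition (1) alone is 1 of 8: never treated, exposed, and outside a low-prevalence area.

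This rests on reading the *or* literally, as it stands in both places, and on the NOTE's own stated purpose of identifying results that may be false.

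The logic is certain and the consequence is small. Harm would need a true infection, a false-negative second test and no later detection, and the documents offer no figures for any of these. Sample size, alpha, power and endpoints are unaffected. It is a cheap improvement worth making, not a threat to the trial's conclusions.

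**What to change.** In the Synopsis and in Section 8.2, reword the condition in the NOTE so that a positive Screening QFT may be regarded as a possible false positive when the patient meets (1) and, in addition, either (2) or (3). Leave the text of the three conditions and the second-test requirement unchanged. Align the eligibility check, so that residence and exposure are recorded for every QFT-positive patient without a history of successful treatment.

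The change stops the never-treated, exposed patient outside a low-prevalence area from reaching the retest. It also closes the retest to successfully treated patients who now reach it through (2) or (3). That follows from making (1) necessary, and it is defensible because their past infection is already known. The sponsor should confirm that it is wanted. Requiring all three conditions is a stricter clinical option that the sponsor may choose, but nothing in the documents calls for it.

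The cost is an amendment to one sentence in two places, with IRB/EC approval before use unless it is classed as administrative (Section 13.4), and an unknown, probably small, number of extra screen failures. The Synopsis estimates the last visit for June 2022, so an amendment may come too late to affect enrolment.
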